## 1 AMENDMENT HISTORY

Amendment No.	Protocol Version No.	Date issued	Author(s) of changes	Details of Changes made

# Formatted: Not Highlight Formatted: Superscript, Not Highlight Formatted: Not Highlight

## 2 SYNOPSIS

Study Title	WOMB: Wearable device to Observe Movements of your
	Baby (WOMB) study
	Baby (Weins) study
	An observational study to investigate the effectiveness and acceptability of a wearable smart garment to independently detect foetal movements in pregnant women
Internal ref. no.	
Type of study	Pre CE marking or Post Marketing Surveillance
Trial Design	Observational study
Trial Participants	Pregnant women weeks 32-38 of pregnancy
Planned Sample Size	54
Follow-up duration	24 weeks
Planned Trial Period	June-December 2021
Primary Objective	To determine the effectiveness of the wearable device in detecting fetal movements, as identified by the operator scanning, compared with those detected by the pregnant women.
Secondary Objectives	To determine the positive-predictive value of the wearable device in detecting foetal movements, compared with the pregnant women.     To establish the acceptability of the device for women
Primary Endpoint	The proportion of movements, as identified by the scan operator, that are successfully detected by the wearable device and the pregnant women (i.e., their sensitivity rates), at weeks 32, 34, 36, and 38 of pregnancy.
Secondary Endpoints	1. The proportion of movements detected by the device and by the pregnant women that are true-positives, that is those that are also identified by the scan operator (i.e., their positive-predictive value rates), at weeks 32, 34, 36, and 38 of pregnancy.  2. Acceptability of wearing the device as self-reported by the women in a bespoke end of study questionnaire.
Device Name	WOMB version 1 device
Manufacturer Name	Kymira
Principle intended use	A garment that can be worn to monitor fetal movements

Version 2 April 12th 2021

Formatted: Not Highlight

Formatted: Superscript, Not Highlight

Formatted: Not Highlight

#### 3 ABBREVIATIONS

AE Adverse event

ADE Adverse Device Effect
CI Chief Investigator

CRF Case Report Form

CRO Contract Research Organisation

CT Clinical Trials

CTA Clinical Trials Authorisation EC Ethics Committee (see REC) GCP Good Clinical Practice GΡ General Practitioner **ICF** Informed Consent Form IEC Independent Ethics Committee IRB Independent Review Board NHS National Health Service

NRES National Research Ethics Service (previously known as COREC)

PI Principal Investigator

PIL Participant/ Patient Information Leaflet

R&D NHS Trust R&D Department
REC Research Ethics Committee
SAE Serious Adverse Event
SADE Serious Adverse Device Effect
SIL Subject Information Leaflet (see PIL)
SOP Standard Operating Procedure

TMF Trial Master File

UADE Unanticipated Adverse Device Effect

Formatted: Superscript, Not Highlight

Formatted: Not Highlight

#### 4 BACKGROUND AND RATIONALE

Fetal movements are reassuring for fetal health. It can be difficult for some woman to appreciate fetal movements and this can lead to unnecessary medical intervention.

We propose to test a thin, flexible textile-like sensor (which is conformable, breathable, and washable) embedded within a wearable garment, KYMIRA will create a solution that is easier and more comfortable for longer term monitoring. Moreover, the wearable will be fully washable, enabling better hygiene and potentially allow 24 hour monitoring.

We aim to correlate objectively measured fetal movements with those detected by the device via real-time imaging of the moving foetus using ultrasound.

We will be monitoring movements over a 20 mins period for women who are between 32-38 weeks of pregnancy. The device will monitor the movements, whilst a scan operator monitors movements and whilst the mother reports movements.

We aim to look at how fetal movements can be monitored in the third trimester using our device and check externally that the device works. We will scan a women 4 times in her pregnancy from 32-38 weeks whilst she is wearing the device. The device will need to be modified for the study so scanning can occur simultaneously.

Other studies have looked into various devices. Often these are bulky, non-washable and require hospital visits. Some use methods, such as picking up the acoustics of fetal movement (Lai J, 2018)). Our device works by using a piezoelectric fabric which essentially generates a tiny voltage when the material is bent or stretched. These studies have also looked at a 20-30min scan period and have shown this is sufficient time to notice movements (Melendez TD, 1992)).

## 5 OBJECTIVES

## 5.1 Primary Objective

To determine the effectiveness of the wearable device in detecting foetal movements, as identified by the operator scanning, compared with those detected by the pregnant women.

#### 5.2 Secondary Objectives

- 1. To determine the positive-predictive value of the wearable device in detecting foetal movements, compared with the pregnant women.
- 2. To establish the acceptability of the device for women.

CONFIDENTIAL

Page 8 of 29

Version 2 April 12th 2021

Formatted: Not Highlight

Formatted: Superscript, Not Highlight

Formatted: Not Highlight

#### TRIAL DESIGN

#### 6.1 Summary of Trial Design

Prospective observational study. The scan operator will be blinded to the movements being detected by the device, and the device data will be processed by a separate independent person. It would involve four 20–30-minute visits. The first visit would include completing the consent and a 20 min scan. We would initially see the woman at around 32 weeks. Then 34, 36, 38 weeks and follow up at 6-8 weeks postnatal with a telephone call. A separate fabric element of the device will be made for each patient, in order to maintain the strictest of hygiene.

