## 6.2 Primary and Secondary Endpoints/Outcome Measures

#### 6.2.1 Primary Endpoints/Outcome Measures

The primary endpoint of the study is the proportion of movements, as identified by the scan operator, that are successfully detected by the wearable device and the pregnant women, at weeks 32, 34, 36, and 38 of pregnancy. These are the sensitivity rates of the device and pregnant women in detecting foetal movements, treating the scan operator detected movements as the "true" movements.

Fetal movement information noted on the scan would be collected by the operator pressing a foot pedal each time a movement is noted. If the movement persists, another event would be recorded. Fetal movements will be defined as any movement noted by the scan operator. Therefore, a combination of both trunk movements and limb movements will be recorded by the scan operator.

Maternal fetal movements noted would be collected by the mum pressing a button when she felt the movement.

The device will collect movements when the piezoelectric fabric is distorted by fetal movements. Maternal movements such as breathing and vessel pulsation will be filtrated out by software.

All three movements, device, maternally perceived and scan operator recorded will be recorded over 20 mins. The data will be time-stamped to allow matching of the movements, allowing for a degree of error (±500ms) to account for the reaction time of the mother and sonographer.

Raw voltage data collected by the device will be processed and converted to binary movements using an independent "training" subset of the data.

CONFIDENTIAL

Page 9 of 29

Version 2 April 12th 2021

Four separate scans will be undertaken 2 weeks apart. We would aim for these to be in 32nd, 34th, 36th, 38th week. With a margin of flexibility of one week.

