#### 7 TREATMENT OF TRIAL PARTICIPANTS

#### 7.1 Description of Study Intervention(s)

The study intervention will involve four ultrasound scans lasting 20 mins during which fetal movements will be recorded. The fabric device will also be worn on the mother's abdomen and will also be recording movement. The mother will also have a button to press when she feels movements.

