## 7.2 Maintenance and storage of device

The device will be in two parts. The fabric wearable part and a separate recording box with its own low power supply and data recording abilities. The fabric part will be new for each patient. The fabric part will be stored in a plastic sealed folder in the research room. Labelled with patients study number, in between scans. The plastic box part will be Clinicel wiped in between each patient. The device will be maintained by Kymira but training will be given to the staff at CUH.

Formatted: Superscript, Not Highlight

Formatted: Not Highlight

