#### 10 DIRECT ACCESS TO SOURCE DATA/DOCUMENTS

Direct access will be granted to authorised representatives from the sponsor, host institution and the regulatory authorities to permit trial-related monitoring, audits and inspections. The electronic data collected by the device will be anonymised by the trial team, with no identifiable data other than the study participant number. Then sent electronically to the device team to analyse.

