## 14 FINANCING AND INSURANCE

KYMIRA will provide funding for this study. The device under test is developed following IEC 62366, ISO 14971 and ISO 13485 for medical device safety, and IEC62304 for medical device software. Following and maintaining these standards is crucial as the proposed medical device product being developed will be classified under Class IIa as defined by the new medical device regulations (EU MDR 2017/745), and Class 2 under the USA's FDA 21 CFR Part 820.

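### Only the operator is blinded, and only to the device: masking between mother and operator and a locked, blind device conversion are not stated, and 6.1 and 10 need reconciling on who processes device data

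*Protocol*

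**What the plan says.** - **Blinding.** Protocol 6.1 holds the only blinding statement: "The scan operator will be blinded to the movements being detected by the device". The same sentence adds that "the device data will be processed by a separate independent person".
- **The reference.** Under 6.2.1 the reference movements are "collected by the operator pressing a foot pedal each time a movement is noted". Anything that the operator regards as a movement counts, so the reference is a matter of judgement.
- **The mother.** Section 7.1: "The mother will also have a button to press when she feels movements". Sections 4 and 6.2.1 have device, operator and mother recording over the same 20 minutes. Section 6.4.5 says that the three sets are recorded separately.
- **The device.** Under 6.2.1 raw voltage is turned into yes/no movements with the help of an independent training subset. Section 9.1.1.1 sets aside 3 women, about 30 movements, for this calibration.
- **Data flow.** Section 10: "The electronic data collected by the device will be anonymised by the trial team", and then "Then sent electronically to the device team to analyse". Section 7.2: "The device will be maintained by Kymira". Section 14: "KYMIRA will provide funding for this study".
- **Primary test.** Section 9.1.1 compares device and mother with McNemar's test on the operator's movements. Section 9.1.1.1 assumes sensitivities of 60% and 44% and asks for 395 movements per visit.

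**The concern.** The primary endpoint compares two detectors against a third observer, so its validity depends on the three working without knowledge of one another. The protocol secures this in one direction only.

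A mother who sees the image or notices the pedal can press for a movement that she did not feel. If the press falls within the ±500 ms matching window, it counts as a detection and raises her sensitivity. An operator who notices her button may pedal to match, which adds reference movements that she has by definition detected. Both effects favour the mother.

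The device side carries a risk in the other direction. Its events are produced by processing, so there is room for choice. If the person who converts the voltage holds the pedal or button times of the analysed women and the method is not yet fixed, those choices can be fitted to the reference, which favours the device. The wording on who that person is does not settle the matter: 6.1 speaks of independence, and section 10 names the device team.

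The difference observed would be the net of these effects, and nothing in the planned data would show how much each had contributed.

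**Working it through.** **1. Which paths does the text close?**

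| Path | What the protocol says | Status |
|---|---|---|
| Device to operator | Operator blinded (6.1) | Closed |
| Device to mother | No live device output to her is described; a separate box records the data (7.2) and the voltage is processed into movements (6.2.1) | No support |
| Screen or pedal to mother | Nothing; 6.4.5 concerns separate recording, not what she can see or hear | Open |
| Mother's button to operator | Nothing | Open |
| Pedal and button times to device conversion | Training subset set apart (6.2.1, 9.1.1.1); section 10 mentions only device data being sent; no lock and no blinding stated for analysed women | Partly guarded |

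**2. Section 6.1 beside section 10.** The first has the device data processed by someone separate and independent. The second has them analysed by the device team. Both hold together if independence means only from the operator and a member of the device team does the conversion. They conflict if it means independence from the manufacturer. The protocol does not say which.

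**3. The plan's own figure.** Inputs from 9.1.1.1: device 0.60, mother 0.44, two-sided 5%, 90% power, minimum phi correlation.

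- Smallest joint detection: p11 = max(0, 0.60 + 0.44 − 1) = 0.04.
- Device only: b = 0.60 − 0.04 = 0.56. Mother only: c = 0.44 − 0.04 = 0.40.
- Discordant share: pd = b + c = 0.96. Difference: d = b − c = 0.16.
- n = (z0.975 + z0.90)² × pd / d² = 10.5074 × 0.96 / 0.0256 = 394.03, rounded up to 395. The plan's figure is reproduced.
- Women: 395/10 gives 40; plus 3 for training is 43; 43/0.80 = 53.75, so 54. Also reproduced.

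**4. What cueing would do (assumption).** Let q be the share of movements the mother does not feel for which she presses because of the scan or pedal, with the press inside the matching window. The documents give no q, so a range is shown. The device stays at 0.60, with 395 movements treated as independent, as the plan does.

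- Apparent maternal sensitivity: m = 0.44 + q × 0.56.
- At minimum phi every movement the mother misses is one the device detects, since the share missed by both is 1 − 0.56 − 0.40 − 0.04 = 0. Cueing therefore moves q × 0.56 from b to joint detection, and c stays at 0.40.
- Power = Φ[(|d|√395 − 1.96√pd) / √(pd − d²)].

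| q | m | b | pd | d | Power |
|---|---|---|---|---|---|
| 0 | 0.440 | 0.560 | 0.960 | 0.160 | 90% |
| 5% | 0.468 | 0.532 | 0.932 | 0.132 | 78% |
| 10% | 0.496 | 0.504 | 0.904 | 0.104 | 59% |
| 20% | 0.552 | 0.448 | 0.848 | 0.048 | 18% |

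The planned difference vanishes at q = 0.16/0.56 = 0.286, about 29%. Above that its sign reverses.

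**5. Tuning of the device conversion.** The documents give no basis for a figure, and none is offered.

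**The case against.** Most of the case on the other side is about how far the text can be pushed, and much of it stands.

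- A reader might infer that all three streams can influence one another. The text does not support this: 6.1 closes the path from device to operator, and no device output to the mother is described.
- A reader might infer that the mother can in fact follow the scan and hear the pedal. Screen position, noise and room layout are not described. They may be set in an operating procedure, to which section 11 refers in general terms, and little of the appendices is visible. All that can be said is that no masking is stated.
- A reader might call 6.1 and 10 a flat contradiction. The sentence in 6.1 is about the operator, and independent may mean only independent of the operator. Nor does section 10 say what the analysis consists of.
- Tuning is not unguarded. Calibration is assigned to separate women, and section 10 read literally sends only data collected by the device. What is missing is narrower: a lock, and blinding of the converter to the analysed women's pedal and button times.
- Cueing works against the device, and so against the result the funder would hope for. It does not produce a spurious finding of device superiority. It still distorts the estimated difference and costs power.

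None of this supplies the missing masking. Separate recording does not stop one observer from reacting to another, and a cued press cannot be told from a felt one once it is recorded.

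**Conclusion.** The concern holds in limited form. The protocol states one blinding rule, operator toward device. It leaves mother and operator unmasked from each other while one supplies a subjective reference and the other the comparator in the primary test. It does not say that the device conversion is locked or blind for the analysed women. Sections 6.1 and 10 are in tension on who does that work and must be reconciled; a proven contradiction, or evidence that the manufacturer tunes to the reference, is more than the text shows.

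On size, cueing of 5% to 20% of unfelt movements would shrink the planned 16-point difference to between 13.2 and 4.8 points, with power of about 78% down to 18%. This rests on an assumed cueing rate, an unchanged device sensitivity of 60%, independent movements and the plan's minimum phi. It illustrates sensitivity to the problem and does not predict how much cueing will occur. The change should be made before the first recording, because it cannot be made afterwards.

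**What to change.** 1. **Sections 6.1 and 7.1.** Turn the screen away from the mother, use a silent pedal and a silent button out of the operator's view, and allow no remarks on movements during the 20 minutes.
2. **Sections 6.2.1 and 10.** For women outside the training subset, release only the voltage trace to the person who converts it. Require locked, time-stamped detections back before pedal and button data are released. Have the hospital team or the statistician do the matching.
3. **Sections 6.1 and 10.** State in both who converts the device data and of whom that person is independent, so that the two sections agree.

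The cost is protocol wording and room set-up, with no extra staff. The one small drawback is that the mother does not watch the scan while recording is under way.

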## 6.2 Primary and Secondary Endpoints/Outcome Measures

#### 6.2.1 Primary Endpoints/Outcome Measures

The primary endpoint of the study is the proportion of movements, as identified by the scan operator, that are successfully detected by the wearable device and the pregnant women, at weeks 32, 34, 36, and 38 of pregnancy. These are the sensitivity rates of the device and pregnant women in detecting foetal movements, treating the scan operator detected movements as the "true" movements.

Fetal movement information noted on the scan would be collected by the operator pressing a foot pedal each time a movement is noted. If the movement persists, another event would be recorded. Fetal movements will be defined as any movement noted by the scan operator. Therefore, a combination of both trunk movements and limb movements will be recorded by the scan operator.

Maternal fetal movements noted would be collected by the mum pressing a button when she felt the movement.

The device will collect movements when the piezoelectric fabric is distorted by fetal movements. Maternal movements such as breathing and vessel pulsation will be filtrated out by software.

All three movements, device, maternally perceived and scan operator recorded will be recorded over 20 mins. The data will be time-stamped to allow matching of the movements, allowing for a degree of error (±500ms) to account for the reaction time of the mother and sonographer.

Raw voltage data collected by the device will be processed and converted to binary movements using an independent "training" subset of the data.

CONFIDENTIAL

Page 9 of 29

Version 2 April 12th 2021

Four separate scans will be undertaken 2 weeks apart. We would aim for these to be in 32nd, 34th, 36th, 38th week. With a margin of flexibility of one week.

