# 6.2.2 Secondary Endpoints/Outcome Measures

The first secondary endpoint of the study is the proportion of movements detected by the device and by the pregnant women that are true-positives, that is those that are also identified by the scan operator, at weeks 32, 34, 36, and 38 of pregnancy. These are the positive predictive values of the device and the pregnant women, which will help understand the extent of false-positive movements and their impact on the usefulness of the wearable device.

The second secondary endpoint of the study is the acceptability of wearing the device as self-reported by the women in a bespoke end of study questionnaire. Please see Appendix 3.

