#### 9 STATISTICS

#### 9.1 Description of Statistical Methods/ Sample size

#### 9.1.1 Analysis of Primary Endpoint

This is a pilot study to test KYMIRA's device on human subjects for the first time, with the primary outcome of interest being its effectiveness in detecting fetal movements, as identified by the operator scanning, compared with those detected by the pregnant women.

The analysis of the primary endpoint will therefore be a comparison of the proportion of movements, as identified by the scan operator, that are successfully detected by the wearable device compared with the proportion detected by the pregnant women, at each of weeks 32, 34, 36, and 38 of pregnancy separately.

The data to be analysed are the binary (Yes/No) outcomes for the device and the mother indicating whether each of the scan operator movements was successfully identified. There will be an outcome for the device and the mother (Yes/No, i.e., Detected/Not detected) for the same scan operator-identified movement. The data are therefore paired and a McNemar's test of paired proportions will be conducted to detect a difference in the proportions of movements detected by the device compared with the mother, if such a difference exists.

The same analysis will be repeated for the week 32, 34, 36 and 38 visit movements separately. The movements at a particular visit (either week 32, 34, 36 or 38) will be collated across the pregnant women for analysis. The repeated foetal movements for a given pregnant woman during a particular scan will be treated as independent.

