## 9.1.1.1 Sample Size Determination

Previous studies that compared the number of fetal movements observed by ultrasound and those perceived by mothers during the 3rd trimester (Brown R, 2016) (Hertogs K, 1979) found the later to be highly varied; with different studies reporting different average fractions in the range of 0.16 to 0.44 (Hertogs K, 1979). Hence, we calculated the sample size for an

CONFIDENTIAL

Formatted: Not Highlight

Formatted: Superscript, Not Highlight

Formatted: Not Highlight

Page 17 of 29

Version 2 April 12th 2021

assumed sensitivity rate of 44% for the pregnant mothers, corresponding with the most conservative estimate, i.e., to ensure adequate power. Based on the initial simulation tests of our device, we expect it to detect 0.8 to 0.9 fraction of the fetal movements. Allowing for a potentially lower detection rate in clinical practice, we assumed a sensitivity rate of 60% for the wearable device, again corresponding a larger sample size to ensure sufficient power.

For a single visit (week 32, 34, 36 or 38), based on a two-sided McNemar's test with a 5% significance level and 90% power, 395 movements are required (according to Lachenbruch (1992) (Lachenbruch, 1992) and based on the minimum estimate of the phi correlation r). Each pregnant woman is expected to have a minimum of around 10 foetal movements per 20 minute scan, as detected by the sonographer, therefore (rounding up) approximately 40 subjects are required for the study analysis.

In addition, an independent "training" subset of the data are required for calibrating the device. It is estimated that 3 subjects will be required for this purpose (i.e., approximately 30 movements), taking the number of subjects in the study to 43. Allowing for a drop-out rate of approximately 20%, a final sample size of 54 subjects (again rounding up) are estimated to be required for recruitment into the study. As the sample size required is based upon the number of foetal movements, if a different number of movements per mother is observed than assumed, the number of subjects recruited will be amended to ensure an appropriate total number of movements available for analysis.

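### The primary test compares sensitivity alone, with no allowance for chance matches, and the PPV result has no bearing on its conclusion

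*Protocol*

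**What the plan says.** The primary objective (Protocol 5.1) is the device's effectiveness in detecting operator-identified movements, compared with the mother. Section 6.2.1 turns this into two proportions: "These are the sensitivity rates of the device and pregnant women in detecting foetal movements", with the scan operator as reference. Events are matched by time stamp within ±500 ms.

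Section 9.1.1 limits the data to yes/no outcomes "indicating whether each of the scan operator movements was successfully identified", and at each of the four visits "a McNemar's test of paired proportions will be conducted". Signals without a matching operator event are not part of these data.

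False detections are taken up in 6.2.2. PPV of device and mother is the first secondary endpoint, "which will help understand the extent of false-positive movements and their impact on the usefulness of the wearable device". Section 9.1.2 compares it by a z-test at the same four visits.

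The protocol states no adjustment for chance matching and no limit on false detections. It does not say how the sensitivity and PPV results combine into a conclusion.

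**The concern.** The two sides of the comparison are not alike. The mother presses a button. The device's events come from a continuous voltage trace converted to yes/no movements, so its firing rate depends on how that conversion is set. In the primary test, extra firing can only help the device: each added event may land in a window and score a detection, and none counts against it.

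At stake is what a significant primary result means. It could reflect better detection of fetal movement, or more frequent triggering. Section 6.2.1 names breathing and vessel pulsation as signals the software must remove, and 9.1.1 describes a first use in humans, so some residual non-fetal triggering is foreseeable.

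**Working it through.** **Inputs from the protocol.** Match window ±500 ms, so 1 second per operator event (6.2.1). About 10 movements per 20-minute (1,200 s) scan, maternal sensitivity 0.44 ("assumed sensitivity rate of 44% for the pregnant mothers"), device sensitivity 0.60 ("we assumed a sensitivity rate of 60% for the wearable device") and 395 movements per visit (all 9.1.1.1).

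**Assumed, not in the protocol.** False-trigger rates of 5, 12 and 20 per minute; triggers random in time; any event in the window counts as a match; windows do not overlap; movements independent, as 9.1.1 treats them.

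**The plan's own figure.** The protocol says: "based on a two-sided McNemar's test with a 5% significance level and 90% power, 395 movements are required". At the minimum phi, the cell probabilities are 0.56 (device only), 0.40 (mother only) and 0.04 (both), so the discordant share is 0.96. Then (1.960 + 1.282)² × 0.96 / 0.16² = 394.03, rounded up to 395. The sample size reproduces and is not at issue.

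**Chance matching.** For r random triggers per minute and a 1-second window, the chance of at least one match is c = 1 − exp(−r/60). A device with true sensitivity 0.44 then shows s = 0.44 + 0.56c.

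**PPV.** With k = 20r false triggers per scan, of which k × 10/1,200 fall in a window by chance, PPV = (4.4 + k × 10/1,200) / (4.4 + k).

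**Chance of winning.** With device and mother independent, the discordant share is D = 0.56s + 0.44(1 − s) and the difference is d = s − 0.44. The probability of a significant result for the device is Φ[(d√395 − 1.96√D) / √(D − d²)].

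| r per min | c | s | PPV | P(device wins) |
|---|---|---|---|---|
| 5 | 0.080 | 0.485 | 5.0% | 24% |
| 12 | 0.181 | 0.542 | 2.6% | 81% |
| 20 | 0.283 | 0.599 | 1.9% | 99% |

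At 12 per minute: D = 0.505 and d = 0.1015, so (2.018 − 1.393) / 0.703 = 0.888 and Φ = 0.81. A simulation of 20,000 trials gave 82%.

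**Dependence on the pairing.** Suppose instead that the true detections of device and mother never coincide, the most negative correlation possible when both are 0.44. At 12 per minute the device-only share is 0.44 + 0.12 × 0.181 = 0.462 and the mother-only share is 0.44 × 0.819 = 0.360, so D = 0.822. The win probability is then Φ[(2.018 − 1.777) / 0.901] = 61%. Positive correlation moves it above 81%.

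**A device with no information.** Random firing alone reaches 0.44 at −60 ln(0.56) = 34.8 per minute and 0.60 at −60 ln(0.40) = 55.0 per minute, with a PPV of 10/1,200 = 0.8%. The protocol also cites "different average fractions in the range of 0.16 to 0.44" for maternal detection. Against a 16% mother, purely random firing wins in 59% of simulated trials at 15 per minute and in practically all at 24 per minute.

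**The case against.** The strongest reply is that the plan already measures false detections. PPV against the mother is the first secondary objective and endpoint, is included for this purpose, and is tested at every visit. At 840 random alarms per scan in 40 women, the planned z-test would exceed 60 in the mother's favour for any assumed maternal PPV from 0.3 to 0.8. That stands. It would be wrong to say that the plan ignores false positives, or that gross over-firing would go unseen.

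Other parts of the reply also stand:

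- The trigger rates are assumptions, and artefact is to be filtered by software. At 5 per minute, chance matching is only 8%.
- A reader might infer that the device will be declared better on sensitivity alone. The protocol writes no such rule; the study is a pilot, and 60% is a planning value, not a success threshold.
- A reader might infer that the sponsor can tune the threshold on the test data. Sections 6.2.1 and 9.1.1.1 provide an independent training subset of about three women, and 6.1 has device data processed by a separate independent person.
- The objective is worded as detection of operator-identified movements, so comparative sensitivity is a fair reading of it.

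Two things are left unanswered. PPV does not take chance matches out of the sensitivity estimates. And the plan is silent on what to conclude if sensitivity favours the device while PPV favours the mother.

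**Conclusion.** The concern holds as a cheap improvement, not as a fatal flaw. The primary comparison is sensitivity only, makes no allowance for chance matches, and is not informed by the PPV result. Over-firing can therefore produce a significant primary result without better information.

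Under the stated assumptions, a device no better than the mother at true detection would show about 49%, 54% or 60% instead of 44% at 5, 12 or 20 random triggers per minute. At 12 per minute it would win about 81% of the time under independence, or about 61% under the most negative pairing.

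A stronger reading, that a device carrying no information would plausibly win, is not supported at the planned 44% maternal rate. That would take an extreme 35 triggers per minute merely to draw level and 55 to reach the planned 60%, and the PPV comparison would show it at once. The practical risk is a permissive setting or residual artefact added to some real detection.

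**What to change.** In section 9.1.1:

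1. Beside each sensitivity, for device and mother, report the chance-expected value and the excess over chance. Obtain it by shifting each event series in time within the scan and re-matching it to the operator events.
2. State that any conclusion that the device is more effective than the mother will rest on sensitivity and PPV read together, not on the sensitivity test alone.

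Neither needs a margin, more women or new data; the time-stamped records suffice. The cost is a few lines of text and a little extra analysis. The downside is that a favourable headline becomes harder to reach.

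Reporting false detections per minute and stating that the conversion rule is frozen before the test data are processed would be useful additions, but these can be left to the SAP.
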